#### **Data handling**

Each subject will be given a unique identifier code at randomisation. All data will be entered into an electronic database by UoSCTU staff (data officers) blinded to the subject's study status. Research staff blinded to the subject's study status will perform all statistical analyses.

BREATHE Page 24 of 35 Protocol v6 01-08-2014

#### Qualitative process evaluation

An open-ended qualitative study will be used to evaluate patient experiences of the trial and identify factors that may have influenced trial outcomes. We will carry out telephone interviews with 12-15 patients in each arm of the trial, purposively sampled for diversity in terms of age, gender, education and symptom profile, and seeking to ensure representation of participants with poor adherence or outcomes. The interviews will be carried out 6 to 8 weeks after baseline and will consist of open-ended questions asking about experiences of the trial, including changes, positive and negative aspects, suggestions for improvement etc. All data will be tape-recorded, fully transcribed and analysed inductively by thematic analysis (28).

#### Health economic evaluation

The resources needed to design and develop the DVD intervention will be recorded during phase 1. During the trial we will also record all resources required to provide the interventions in the DVD and the 'face-to-face' physiotherapy groups. Information will also be collected on all asthma-related healthcare costs for the 1-year follow up period. These will be collected using medical records to collect all asthma related NHS service use (primary and secondary care patient contacts, investigations and prescriptions) with maximum possible use of electronic records, supplemented where necessary by paper records. Respondent questionnaires will be completed at 3 month and 12 month data collection points to quantify time off work/college; and out of pocket expenses. This will constitute a societal perspective to the analysis.

Resources will be costed using appropriate local and national cost data. Total NHS and societal costs will be estimated for each group allowing estimates of the incremental costs of the breathing DVD and 'face-to-face' physiotherapy programmes compared to usual care. Health related quality of life will be assessed using the EuroQol (EQ5D) collected at baseline, 3, 6, and 12- months. These EQ5D scores will be used to generate quality adjusted life years (QALYs). No mortality differences are expected. The superiority analyses will include a cost-utility study (cost per QALY) and cost-effectiveness (cost per significant change in asthma-related health status, i.e. a change of 0.5 in the AQLQ score). If non-inferiority is proven between the face-to-face and DVD interventions, cost minimisation will be carried out. Where appropriate, incremental costeffectiveness ratios (ICERs) and cost-effectiveness acceptability curves (CEACs) will be estimated. Sensitivity analysis will be used to test any major assumptions made in the costing/analysis process. We will check for the extent of missing data at the analysis stage. If considered necessary, we will use appropriate statistical methods (for example multiple imputation) to impute missing data. This will be presented as a sensitivity analysis, i.e. in addition to the complete case analysis.

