#### **Secondary Objectives:**

- To perform a qualitative process evaluation on 12-15 subjects in each arm of the trial, purposively sampled for diversity
- To estimate the cost-effectiveness of the breathing retraining interventions delivered by DVD and by face-to-face instruction, using data collected from the trial and from the GP held clinical records
- To perform an initial 'internal pilot' in 2 centres to confirm recruitment targets and protocol viability, and subsequently to extend recruitment to further centres (approximately 20)

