#### 1. For equivalence of DVD programme and face-to-face programme.

In a previous HTA study comparing different pharmacotherapy options in asthma (the ELEVATE study, Controlled-Trials.com number, ISRCTN99132811, Price et al, 2011), treatments were deemed to be equivalent if the 95% CI for mean difference between groups in AQLQ was wholly included between -0.3 and +0.3. Our sample size calculation for equivalence therefore uses the same equivalence boundary (i.e. between -0.3 and +0.3). However, we have assumed that the SD of the between group difference in AQLQ will be a conservative 25% smaller (i.e. 0.77) than that reported in our GLAD study (1.03). The justification for this is that the proposed equivalence analysis will compare two breathing training interventions as opposed to a breathing intervention versus usual care in the GLAD study. Since this is an equivalence study, as opposed to a non-inferiority study, a two-tailed 5% significance level was used in the calculations (29). Following published guidelines (30), the equivalence margin was therefore selected to be 'the largest difference that can be judged to be clinically acceptable and should be smaller than differences observed in superiority trials of the active comparator'.

Using Nquery 7.0 (specifically the MTEOU-1 two group t-test of equivalence in means – unequal n's program), the following justification of the sample size is obtained:

Sample sizes of 210 in the DVD breathing retraining group and 105 in the 'face-to-face' physiotherapy group are required to assess treatment equivalence with 90% power using an equivalence boundary for AQLQ of 0.3. This assumes: that the expected between group difference in mean AQLQ is zero; a two tailed 5% significance level; common standard deviation for AQLQ of 0.77 and a lower/upper limit of -0.3/+0.3 for the 95% confidence interval of the between group difference in AQLQ.

In the unlikely event that the between group AQLQ standard deviation is higher than our estimated 0.77, assuming all other parameters stayed the same, we would still have 80% power to declare equivalence between the DVD breathing retraining group and the 'face-to-face' physiotherapy group as long as the between group SD was no higher than 0.89.

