#### Statistical Analysis:

#### 1. Analysis plan for equivalence study

Analysis and reporting of the equivalence comparison will follow published guidelines. It is known that full analysis set or ITT may lead to bias (from protocol violators, withdrawals and dropouts) and a resultant increase in type 1 error risk. Therefore, for the equivalence study, an ITT and a per protocol analysis will run simultaneously, neither having supremacy over the other. They should hopefully lead to similar conclusions giving the study a robust interpretation.

A 95% CI will be constructed for the mean difference in 12 month total AQLQ score between the DVD arm and the 'face-to-face' breathing retraining arm. Since the equivalence boundary is set at 0.3, equivalence will be declared if the 95% CI is wholly included between -0.3 and +0.3. If equality is not evident, then ANCOVA will be used to examine whether the 'face-to-face' breathing retraining arm is superior to the DVD arm via examination of the difference (and 95% confidence interval) of 12 month total AQLQ score (and each of the four domain scores) before and after adjustment for baseline AQLQ score and potential covariates such as age, gender, practice, smoking status etc.

BREATHE Page 27 of 35 Protocol v6 01-08-2014

ANCOVA will also be used to analyse the difference (and 95% confidence interval) for the secondary outcome measures (ACQ, lung function, fraction of exhaled nitric oxide, EuroQOL, anxiety and depression score, hyperventilation and patient enablement scores) at 12 months before and after adjustment for baseline values and potential confounders. Since we have data on AQLQ, ACQ and HADS at four time points (baseline, 3, 6 and 12 months) a repeated measures analysis will be used to examine change in each of these outcomes over time. For those secondary outcomes which involve count data (i.e. oral corticosteroid courses, bronchodilator use, asthma related healthcare resource use), Poisson regression analyses with a log link function will be performed to give rate ratios (and their 95% confidence intervals) in the DVD and 'face-to-face' breathing retraining arm both before and after adjustment for potential confounders such as smoking status and sociodemographic factors.

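### The DVD v face-to-face economic analysis is triggered by non-inferiority, for which the protocol has no rule, and the only analysis it names is cost minimisation

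*Protocol*

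**What the plan says.** Protocol section 7, Health economic evaluation, sets the condition for comparing the two breathing programmes economically: "If non-inferiority is proven between the face-to-face and DVD interventions, cost minimisation will be carried out". Cost per QALY and cost per 0.5 change in AQLQ are placed elsewhere: "The superiority analyses will include a cost-utility study". The incremental costs it names are those of each programme against usual care. A general sentence then allows ICERs and CEACs where appropriate, without naming comparisons. QALYs come from EQ-5D at baseline, 3, 6 and 12 months, with no restriction by arm.

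Protocol section 8.1, sample size part 1, describes the clinical comparison of the same two arms: "Since this is an equivalence study, as opposed to a non-inferiority study". The margin enters the calculation as "using an equivalence boundary for AQLQ of 0.3".

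Protocol section 8.1, Analysis plan for equivalence study, gives the decision rule: "equivalence will be declared if the 95% CI is wholly included between -0.3 and +0.3". If that is not met, the next step is stated: "If equality is not evident, then ANCOVA will be used to examine whether the 'face-to-face' breathing retraining arm is superior to the DVD arm". ITT and per-protocol analyses are run with equal standing.

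The secondary objectives in the synopsis include this one: "To estimate the cost-effectiveness of the breathing retraining interventions delivered by DVD and by face-to-face instruction".

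**The concern.** The economic section relies on a conclusion for which the statistical section has no rule. No non-inferiority margin, confidence level or analysis set is given anywhere, and the statistical section expressly sets non-inferiority aside. An analyst must therefore decide afterwards whether the condition means the equivalence rule or one limit of the same interval. When those give different answers, the choice decides whether cost minimisation is done.

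The second issue is the method attached to the trigger. Cost minimisation drops the effect side of the comparison and its uncertainty. The condition rests on mean AQLQ at 12 months, whereas QALYs are built from a different instrument over four time points. A mean AQLQ difference inside 0.3 does not show that the QALY difference is zero or negligible.

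At stake is whether the DVD is an economic substitute for face-to-face sessions. The background section makes this a central reason for the trial. The primary clinical analysis is not affected.

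**Working it through.** **Inputs** (Protocol section 8.1): n = 210 (DVD) and 105 (face-to-face); SD 0.77; margin 0.3; expected difference 0; 95% CI. SD 1.03 is the figure from the earlier breathing-exercise trial, which the protocol reduces to 0.77 for this comparison. *Assumptions not in the protocol:* non-inferiority means that the lower 95% limit of DVD minus face-to-face lies above -0.3 (one-sided 2.5%, same margin); true differences other than 0 are illustrative.

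**Step 1. Standard error.** SE = SD × √(1/210 + 1/105) = 0.77 × 0.1195 = 0.0920.

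**Step 2. The protocol's own power figures.** It states 90% at SD 0.77 and 80% at SD 0.89.

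Normal approximation at SD 0.77 and true difference 0: 0.3/0.0920 = 3.26, and 3.26 − 1.96 = 1.30.
- Non-inferiority: Φ(1.30) = 0.903.
- Equivalence: 2 × 0.903 − 1 = 0.806.

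With the t distribution (313 df):

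| SD | Equivalence (95% CI within ±0.3) | Non-inferiority (one-sided 2.5%) | Stated |
|---|---|---|---|
| 0.77 | 80.3% | 90.1% | 90% |
| 0.89 | 60.6% | 80.3% | 80% |

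The stated figures fit the non-inferiority test and not the stated equivalence rule. That is a separate matter, but it shows that the two concepts are mixed elsewhere in the plan too.

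**Step 3. When the rules disagree.** Equivalence needs both limits inside ±0.3; non-inferiority needs only the lower one. So equivalence implies non-inferiority, and they part only when the interval crosses +0.3 alone, the side favouring the DVD.

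P(disagree) = P(non-inferiority) − P(equivalence).

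For a true difference of +0.1 by the normal approximation:
- Lower limit clears −0.3: Φ(0.4/0.0920 − 1.96) = Φ(2.39) = 0.991.
- Upper limit clears +0.3: Φ(0.2/0.0920 − 1.96) = Φ(0.21) = 0.584.
- Equivalence = 0.991 + 0.584 − 1 = 0.576, so disagreement = 0.991 − 0.576 = 0.416.

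With the t distribution, SD 0.77:

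| True DVD − face-to-face | Equivalence | Non-inferiority | Disagree |
|---|---|---|---|
| −0.1 | 57.3% | 58.2% | 0.9% |
| 0 | 80.3% | 90.1% | 9.9% |
| +0.1 | 57.3% | 99.1% | 41.8% |
| +0.2 | 19.0% | 100.0% | 81% |

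At SD 1.03 and true difference 0, equivalence is 36.1% and non-inferiority 68.1%, so they disagree in about 32%.

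**Step 4. What the economic text covers.** Cost per QALY sits in the superiority analyses. The sample-size section and the Analysis plan for superiority study use that term for each programme against usual care. The only analysis expressly attached to DVD v face-to-face is cost minimisation. The sentence on ICERs and CEACs names no comparison. The fallback in the equivalence analysis plan is a superiority comparison of these two arms, but it asks whether face-to-face is better. That fits poorly with the disagreement region, where the data lean towards the DVD.

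**The case against.** The strongest reply is that this is a slip of terminology. The planned 95% CI yields a non-inferiority conclusion from its lower limit, so the condition is mislabelled rather than unattainable. That stands: it would be wrong to say the trial cannot produce the result. The slip still has consequences, because the two readings differ in about 10% of trials even at a true difference of 0.

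A second reply is that preferring cost-utility to cost minimisation disputes a prespecified option and shows no error, and that the detail may sit in an analysis plan not shown. The protocol does not say that QALYs will be set equal or left unanalysed. That is fair, but the protocol positively fixes cost minimisation as what follows, so this choice has not been left open.

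A reader might infer more: that if equivalence fails, no economic comparison of DVD with face-to-face is specified, and that this would happen in about 20% (SD 0.77) to 64% (SD 1.03) of trials. The documents do not support that. Those percentages are the chance of missing equivalence, whereas the written trigger is non-inferiority, missed in about 10% to 32%. SD 1.03 is also not the protocol's assumption for this comparison. And missing the trigger does not mean no analysis: ICERs and CEACs are allowed where appropriate, costs are totalled for every group, the fallback could count as a superiority analysis, and the objective covers both delivery modes.

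**Conclusion.** The point holds in two parts. First, the trigger in the Health economic evaluation contradicts section 8.1 and has no decision rule. With 210/105, SD 0.77 and one-sided 2.5% non-inferiority at the 0.3 margin, the two readings disagree in about 10% of trials at true difference 0 and about 42% if the DVD is truly 0.1 better. If the DVD is truly 0.1 worse they almost never disagree (0.9%). Second, cost minimisation is a weak choice for this comparison, because an AQLQ result within 0.3 does not establish equal EQ-5D QALYs and the data for a joint analysis are collected in all arms. The documents give no figure from which the possible QALY difference could be sized.

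The absence of a DVD v face-to-face cost-utility analysis is a lack of explicit specification and not an exclusion. The matter concerns a secondary objective and should be corrected; it leaves the primary result untouched.

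**What to change.** In the Health economic evaluation, replace the non-inferiority condition with the equivalence rule of section 8.1, and say whether ITT, per protocol or both must meet it. Specify an incremental cost-utility analysis that estimates costs and QALYs jointly, with an ICER or net benefit and a CEAC, and that includes DVD v face-to-face whatever the AQLQ equivalence result. Keep cost minimisation, if wanted, as a secondary presentation only.

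The cost is a little more analysis. EQ-5D and cost data are already collected, and the methods are already planned for the comparisons with usual care.

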- Physiological measurements: Spirometry (FEV1, FEV1/FVC ratio, PEFR), measured with standardized calibrated portable spirometer; Fraction of exhaled nitric oxide (FENO), measured with Aerocrine Mino portable monitor.

If a clinical assessment of potentially dangerous or unstable asthma is made by the trained study nurse, the subject will not enter the study but will be referred urgently back to their usual primary care asthma clinician. Participants who score greater than or equal to 16 in the HADs Questionnaire will be sent a letter from the trial team advising that they may wish to discuss this with their GP. When informed consent has been provided and the baseline assessment completed, the study nurse will telephone UoSCTU for randomisation (or use the web based system when in place). Those randomised to 'usual care' will be informed that they will be posted questionnaires in 3 and 6 months' time to complete and return to the study co-ordinator, and that a final assessment visit will be scheduled for 12 months post randomisation. Contact information will be provided. Those randomised to the DVD intervention will be provided with the written instructional material developed in phase 1 and the DVD. For those who do not have a DVD player at home, an inexpensive DVD player will be provided; it is however anticipated that most people will have access to one of these media players. Subjects will be given information that they will be posted questionnaires in 3 and 6 months to complete and return to the coordinator, and that a final assessment visit will be scheduled for 12 months. Contact information will be provided. For those randomised to the 'face-to-face' physiotherapy arm, they will be informed that they will receive 3 short sessions of contact with a respiratory physiotherapist for breathing retraining. These sessions will be approximately 30-40 minutes long and will occur at roughly 2 weekly intervals following randomisation. The retraining can occur at either the GP surgery, clinic setting or the patient's home according to convenience and preference. The content of the retraining programme

BREATHE Page 18 of 35 Protocol v6 01-08-2014

will be based on those shown to be effective in recent studies (16-18), and similar to the content of the DVD intervention.

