#### 2. Analysis plan for superiority study

Baseline comparability between the three arms of the trial will be evaluated by examination of summary statistics (the mean and standard deviation or median and interquartile range for continuous variables, dependent on their distribution, and the number and percentage for categorical variables). In accordance with CONSORT guidelines, all comparative analysis will be conducted on an intention to treat (ITT) basis with a per protocol analysis performed as a sensitivity analysis.

For the primary outcome, analysis of covariance (ANCOVA) will be used to examine the 12-month total AQLQ score (and each of the four domain scores) across the three arms with initial adjustment for baseline AQLQ score and then for other potential covariates such as age, gender, practice, smoking status etc. Pair wise comparisons of AQLQ differences will be examined between the 'usual care' arm and each of the DVD and 'face-to-face' breathing retraining arms via calculation of one sided 95% confidence intervals. If the confidence interval includes +0.3 then superiority of either the DVD or 'face-to-face' breathing retraining arms over usual care will be rejected.

In a similar way, ANCOVA will also be used to analyse the continuous secondary outcome measures (ACQ, lung function, fraction of exhaled nitric oxide, EuroQOL, anxiety and depression score, hyperventilation and patient enablement scores). Since we have data on AQLQ, ACQ and HADS at four time points (baseline, 3, 6 and 12 months) a repeated measures analysis will be used to examine change in each of these outcomes over time. The 'usual care' arm will be compared to each of the DVD and 'face-to-face' breathing retraining arms in turn.

For those secondary outcomes which involve count data (i.e. oral corticosteroid courses, bronchodilator use, asthma related healthcare resource use), Poisson regression analyses with a log link function will be performed to give rate ratios in the DVD and 'face-to-face' breathing retraining arm compared to 'usual care' both before and after adjustment for potential confounders such as smoking status and sociodemographic factors.

BREATHE Page 28 of 35 Protocol v6 01-08-2014

Data and all appropriate documentation will be stored for a minimum of 5 years after the completion of the trial, including the follow-up period.

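### The economic evaluation takes complete cases as its reference and treats imputation as an optional extra, although the QALY needs every EQ-5D wave

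*Protocol*

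**What the plan says.** The relevant text is in Protocol section 7, under the health economic evaluation. The extent of missing data is to be examined at the analysis stage, and then: "If considered necessary, we will use appropriate statistical methods (for example multiple imputation) to impute missing data". The next sentence fixes the standing of that analysis: "This will be presented as a sensitivity analysis, i.e. in addition to the complete case analysis". Complete cases are thus the reference result. Imputation is conditional and secondary, and no threshold triggers it.

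On the outcome data, the same section says: "Health related quality of life will be assessed using the EuroQol (EQ5D) collected at baseline, 3, 6, and 12- months". These scores are turned into QALYs. NHS service use is taken from medical records. For the societal view, "Respondent questionnaires will be completed at 3 month and 12 month data collection points to quantify time off work/college; and out of pocket expenses".

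Section 7 also describes follow-up of non-responders. At 3 and 6 months all questionnaires are posted, with one postal reminder and then one telephone call or email. At that point the participant may complete the mini-AQLQ by telephone; EQ-5D is not mentioned. At 12 months there is a nurse visit, with one reminder letter and a postal option for those who do not respond.

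**The concern.** A QALY over 12 months combines several EQ-5D measurements, so under listwise deletion one missed return removes the whole person. The follow-up procedure makes this more likely for EQ-5D than for AQLQ at the two postal waves, because only the mini-AQLQ can be recovered by telephone.

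Consider a participant who does not return the 3-month pack, gives the mini-AQLQ by telephone, returns the 6-month pack and attends at 12 months. That person has the 12-month AQLQ and is in the primary clinical analysis. EQ-5D is available at baseline, 6 and 12 months, and NHS costs can be read from the records. The complete-case cost-utility analysis uses none of this.

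Two things are at stake. Precision is lost on data already collected. The cost-utility result may also rest on the participants who reliably return questionnaires, so that it differs from the clinical result partly because of who is included. In addition, whether imputation is done at all is decided after the data have been seen.

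**Working it through.** **Inputs from the protocol**
- Analysed 210, 210 and 105; dropout 10%; recruited 234, 234 and 117, total 585 (section 8.1, Summary).
- Follow-up EQ-5D waves: three, at 3, 6 and 12 months (section 7).
- Baseline EQ-5D is taken as complete, because section 4.1 places it before allocation: "When informed consent has been provided and the baseline assessment completed, the study nurse will telephone UoSCTU for randomisation".

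**Input not given**
- EQ-5D non-response per wave, *m*. Assumed range: 5% to 20%.

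**The plan's own figure.** 210 / (1 − 0.10) = 233.3, rounded up to 234. 105 / (1 − 0.10) = 116.7, rounded up to 117. 2 × 234 + 117 = 585, as stated. The planned loss is (585 − 525) / 585 = 60 / 585 = 10.3%. The protocol states no complete-case fraction for QALYs, so there is nothing to reproduce on that point.

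**Share lost to a complete-case QALY**, with the same *m* at all three waves:
- same people missing each time: *m*
- independent waves: 1 − (1 − *m*)³
- no overlap: 3*m*

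| *m* per wave | Same people | Independent | No overlap | Kept of 585, independent |
|---|---|---|---|---|
| 5% | 5% | 14.3% | 15% | 502 |
| 10% | 10% | 27.1% | 30% | 426 |
| 15% | 15% | 38.6% | 45% | 359 |
| 20% | 20% | 48.8% | 60% | 300 |

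At *m* = 10% with no overlap, about 410 of 585 remain. In the smallest arm, independent waves would leave 117 × 0.9³ = 117 × 0.729, or about 85.

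**Partial overlap.** Suppose 10% are missing at 12 months, the same 10% miss both postal waves, and the two groups are independent. The loss is 1 − 0.9 × 0.9 = 19%. With 20% missing both postal waves it is 1 − 0.9 × 0.8 = 28%.

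**What a loss of one quarter would require.** Independent waves: *m* = 1 − 0.75^(1/3) = 9.1%. No overlap: *m* = 0.25 / 3 = 8.3%. Same people each time: *m* = 25%.

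The cost questionnaires fall at 3 and 12 months, at the same contacts as EQ-5D. They add to these losses only in the societal analysis, and only where EQ-5D was returned and the cost form was not.

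**The case against.** The case on the other side has real weight.

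- **Size.** A reader might infer that a quarter or more of participants will be lost. The protocol does not support that. Its only attrition figure is 10%, dropout accumulates in the same people, and this pushes the loss towards the low end. This stands.
- **Cost data.** A reader might infer that every economic result needs both cost questionnaires. It does not. NHS costs come from records, the questionnaires serve the societal perspective only, and the cost per clinically relevant AQLQ change does not need four EQ-5D waves. This stands.
- **ITT.** A reader might see a contradiction with section 8.1, under the superiority analysis plan: "all comparative analysis will be conducted on an intention to treat (ITT) basis". That sentence sets ITT against per protocol and does not say how missing outcomes are handled. The planned ANCOVA of 12-month AQLQ states no imputation either, and different numbers for different outcomes are normal. The conflict is weak, and the point does not rest on it.
- **Validity of complete cases.** Complete-case analysis is not biased merely because completers differ from non-completers. Adjustment for covariates that explain the missingness can be enough. This stands.
- **Preference only.** Both analyses are already foreseen, so it can be said that only their order is in dispute, and that imputation detail belongs in an analysis plan not shown here. This does not stand in full. The protocol itself fixes the order and does not commit to the second analysis. For an outcome that needs several waves, the order decides whether partial data are used in the main result.

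**Conclusion.** The point holds as a cheap improvement to a stated method, not as an error that endangers the trial. The protocol makes complete cases the reference for a multi-wave outcome and leaves imputation conditional. Base case is a fair description of that position, but it is not the protocol's own term.

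If 10% were missing at each follow-up wave, the complete-case loss would run from 10% (same people), through about 27% (independent), to 30% (no overlap). Overlap between waves is usual and favours the lower end. Postal EQ-5D without telephone recovery could instead push the rate per wave above 10%. All of this rests on an assumed non-response rate, since the protocol gives none, and on a complete baseline. Neither the amount nor the direction of any bias can be derived from the document.

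Cost-effectiveness is a secondary objective, and the clinical primary analysis is unaffected.

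**What to change.** In the health economic evaluation (Protocol section 7):

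1. Make the multiply imputed analysis of all randomised participants the main cost-utility analysis. Impute by arm, using all observed EQ-5D, AQLQ, cost and baseline data.
2. Delete the condition that leaves imputation to a judgement at the analysis stage.
3. Report the complete-case analysis as a sensitivity analysis.
4. Add one simple departure-from-MAR sensitivity analysis, for example shifting the imputed EQ-5D values by arm over a stated range.

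**Cost.** An edit to the text, an imputation model and one further sensitivity analysis. No new data, visits or participants are needed, and the first three steps reorder analyses that are already foreseen. The downside is that the main result then relies on a missing-at-random model. Agreement with complete cases would not test that model, which is why the fourth step is needed.
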